The experiment will consist of four days. Day 1 will include informed consent, questionnaires, a behavioral approach test with a spider, a series of short exposures with a spider, and the first TMS treatment (for a total of approximately 75-90 minutes). Day 2 will occur one to two days after Day 1 and will consist of a second series of short exposures with a spider and the second TMS treatment (30 minutes). Day 3 will occur one to two days after Day 2 and will also consist of a series of short exposures and a TMS treatment (30 minutes). Day 4 will occur five to seven days after Day 3 and will consist of post-study questionnaires and an identical behavioral approach test as is conducted on the first visit (30 minutes). Participants will be randomized to either an active TMS treatment group (using an iTBS stimulation protocol over the participant's ventro-medial prefrontal cortex, an area involved in phobic response) or a control TMS treatment group (using the same iTBS stimulation protocol over the central sulcus and between hemispheres, a site not associated with memory or fear response).

Prospective participants will be undergraduate students recruited through the UCLA Psychology Department Subject Pool (i.e., SONA). At this time, this small pilot study is not equipped to recruit from the population at-large, and therefore is currently limited to recruitment through SONA. All prospective participants will be screened with the 31-question Spider Phobia Questionnaire (SPQ) to ensure eligibility for participation, with a minimum total score equal to or greater than 17 required for participation.(Klorman, Weerts, Hastings, Melamed, & Lang, 1974) Participants will be enrolled for the study only if they are able to complete all four visits of the experiment. Exclusion criteria will include:

1) Subject is mentally or legally incapacitated, unable to give informed consent.

- 2) Subjects with psychosis (psychotic depression, schizophrenia, or schizoaffective diagnoses (lifetime)); bipolar disorder (lifetime); dementia (lifetime); delirium within the past 6 months; eating disorder within the past year; obsessive-compulsive disorder (lifetime); post-traumatic stress disorder within the past year; acute risk for suicide or self-injurious behavior. Patients with diagnostic uncertainty or ambiguity (e.g. rule-out pseudodementia of depression) will be excluded.

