Next, all participants will engage in a series of exposure practices with a different live tarantula from the one they saw during the BAT. Exposure therapy will consist of a series of 10 identical exposure trials of a 30-second duration with a 30-second pause between trials. Participants will be asked to place an ungloved hand in the terrarium (with all fingertips touching the base of the terrarium) on the opposite end of the terrarium as the tarantula during the trial. Prior to completing the series of exposures, participants will be asked about their feared outcome concerning approaching the tarantula (e.g., being bitten). Participants are entitled to withdraw at any step during exposures and will not be prevented from further continuation in the study.

Following the series of exposures, participants will undergo TMS treatments using an iTBS protocol. Before the first iTBS treatment, the TMS coil will be calibrated to the subject's individual resting motor threshold (RMT), or the minimum stimulus intensity necessary to elicit a motor response in the right abductor pollicis brevis (APB) or first dorsal interosseus (FDI) muscles for ≥ 50% of stimuli applied to the motor cortex. After initial calibration, the TMS coil will be placed over the subject's ventral medial prefrontal cortex (vmPFC; as determined using position Fpz of the international 10-20 EEG electrode system), a TMS target shown to affect phobic response.(Baeken et al., 2010; Guhn et al., 2012, 2014; Suarez-Jimenez et al., 2018) Stimulation intensity of 100% of the individual RMT in bursts of three pulses at a frequency of 50 Hz every 200 ms on top of a 5Hz carrier wave. Pulse delivery is over 2 s and repeated every 10 s, 20 times in succession, for a total of 600 pulses delivered in 3.33 minutes.(Baeken et al., 2010; Bulteau et al.,

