2017; Guhn et al., 2014) This specific protocol was selected based on the assumption that it should impact fear circuitry top-down from prefrontal to subcortical networks (particularly the amygdala) as seen in prior work. (Baeken et al., 2010; Bulteau et al., 2017; Guhn et al., 2014) Control iTBS will consist of the same stimulation parameters over the subject's midline central sulcus or vertex (as determined using position Cz, of the international 10-20 EEG electrode system). This placement was chosen for control as its position over the vertex will minimize amount of cortex stimulated and the stimulated area is not associated with the circuitry examined in this experiment. (Duecker & Sack, 2015) It is a commonly-used control site in TMS studies because it is associated with no known effects and has a similar risk profile to other TMS sites. (Foltys et al., 2001; Jung, Bungert, Bowtell, & Jackson, 2016; Rossi et al., 2009; Weiss, Sparing, Fink, Tomasino, & Dafotakis, 2008) It is generally associated with lower rates of scalp discomfort and no clinically-observed behavioral or mood effects. (Jung et al., 2016; Rossi et al., 2009) Some work has demonstrated a possible decrease in activation of the default mode network though this has not been found to be clinically-significant. (Jung et al., 2016)

DAY 2

As described above, this visit will occur one to two days after Day 1. All participants will return to the laboratory to engage in a second series of exposure practices with the same tarantula from exposures at the first visit. They will undergo 10 identical exposure trials for durations of 30 seconds each, with a 30-second pause between trials. During each exposure trial, they will again be asked to place an ungloved hand in the terrarium (with all fingertips touching the base of the terrarium) on the opposite end of the terrarium as the tarantula during the trial. Prior to completing the series of exposures, participants will be asked about their feared outcome concerning approaching the tarantula (e.g., being bitten). Participants are entitled to withdraw at any step during exposures and will not be prevented from further continuation in the study.

Following the series of exposure practices, participants will undergo a TMS treatment using an iTBS treatment protocol in the same location that they received stimulation on Day 1 (vmPFC vs. vertex).

DAY 3

This visit will be identical to Day 2, and will occur one to two days after Day 2.

DAY 4

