This visit will occur five to seven days after Day 3. All participants will complete the Spider Phobia Questionnaire (SPQ; Klorman et al, 1974) and Fear of Spiders Questionnaire (FSQ; Szymanski & O'Donohue, 1995), uploaded in Section 10.1, Item 1.0, to test for change in arachnophobia fear/avoidance symptoms as a function of TMS treatment received. Next, all participants will complete an identical BAT to that completed at their first visit with the same tarantula (see DAY 1 above). Self-report and physiological (i.e., SCR) data will again be collected. After completion of these forms, participants will be debriefed by an un-blinded member of the study team and informed to which group they are assigned. They will be

encouraged to discuss whatever questions or concerns they have regarding the study at that time.

After completion of Day 4, participants will be compensated for their time with one credit per hour of study participation.

Dependent variables (DVs) will be quantitative self-reports and behavioral symptoms of fear and avoidance of spiders both pre- and post-treatment, including SCR (difference between baseline and average level during BAT anticipation period, and number of peaks during BAT), total number of steps completed during the BAT, self-reported distress, anticipatory distress, and maximum distress per BAT step, and total score on the SPQ. BAT measures will be collected for each step and therefore minima, maxima, and means will be compared between the two groups. Primary outcomes examined will be number of steps completed during BAT, self-reported distress during BAT, number of SCR peaks during BAT, SPQ score, and FOS score. All other variables examined will be secondary outcomes. Additionally, for feasibility and tolerability assessment, attendance to TMS treatment sessions and early termination of TMS treatment sessions will be recorded. The primary independent variable examined will be the treatment group (iTBS vs. control iTBS). The sample size will be 40 participants (20 per group). Pre-comparison ANOVA will be performed to limit type 1 error due to multiplicity of comparisons.

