Hypotheses will be tested using between-group two-tailed t-tests given that we are testing not only for magnitude of an effect, but also direction of an effect. We expect that comparisons of efficacy will demonstrate increased confidence during BAT approach, decreased endorsed fear of spiders as measured by SPQ and FSQ, and reduced physiologic response to stimulus (reduced HRV and SCR) with active iTBS and exposure when compared to control iTBS and exposure. We expect that comparisons of feasibility and tolerability will show no significant difference between attendance to, early termination of, or subjective tolerability ratings of TMS treatment sessions between treatment groups.

NOTE 2/2/21: the above reported statistical analysis plan was modified given the small sample size, technical limitations, and distributions of the data observed. The number of statistical tests performed was minimized and multi-level mixed-effects models (MLMs) and nonparametric tests were utilized as appropriate based on the sample size of the experiment. Behavioral measures acquired during the BATs (anticipatory distress, maximum distress, mean skin conductance at each step) were examined using MLMs in Stata version 16.1 as functions of BAT step, group assignment, and timepoint (pre or post-treatment). All other analyses were performed in SPSS (version 26.0.0.0). Demographics and experimental parameters were analyzed for between-group differences using 2-sided Mann-Whitney U Tests. Changes in self-reported fear of spiders (SPQ and FOS) were analyzed using a repeated-measures MANOVA (Greenhouse Geisser correction was applied in case of non-sphericity). A pair of chi-square analyses were performed to validate blinding of the study (based on questionnaires completed by subjects and raters), and no significant deviation from 50/50 chance was observed. A p-value of <0.05 was considered significant for all testing.

ADVERSE EVENT MANAGEMENT

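### Telling each participant their allocation at their own Day 4 visit creates an avoidable risk of unblinding participants who have not yet finished

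*Combined protocol and SAP*

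**What the plan says.** - **Disclosure.** The DAY 4 section places the reveal at the end of each participant's own last visit, once that person's questionnaires and BAT measures are in: "participants will be debriefed by an un-blinded member of the study team and informed to which group they are assigned". No condition ties this to the rest of the sample having finished.
- **Recruitment.** The OVERVIEW states "Prospective participants will be undergraduate students recruited through the UCLA Psychology Department Subject Pool", and that the pilot "therefore is currently limited to recruitment through SONA".
- **What distinguishes the arms.** Under DAY 1, the active coil is placed over the vmPFC, "as determined using position Fpz of the international 10-20 EEG electrode system". For the other arm, "Control iTBS will consist of the same stimulation parameters over the subject's midline central sulcus or vertex", located at Cz. Exclusion criterion 9 also refers to the device sitting on the forehead.
- **Outcomes.** The DAY 4 section lists five: "Primary outcomes examined will be number of steps completed during BAT, self-reported distress during BAT, number of SCR peaks during BAT, SPQ score, and FOS". FOS is read here as the FSQ.
- **Blinding check.** The note dated 2/2/21 reports: "A pair of chi-square analyses were performed to validate blinding of the study". It used subject and rater questionnaires and found no significant departure from an even split. No counts are given.

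**The concern.** Both arms receive the same pulses, and participants can tell where the coil sits. The participant blind therefore depends on not knowing which site is the active one. A participant who is told their group at Day 4 already knows their own coil site and can put the two together. With only two arms, one such report, from either arm, decodes both.

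The people at risk are those who have not completed Day 4 when someone else is debriefed. They share a subject pool with the person who has just been told. Four of the five primary outcomes are self-reported or under the participant's control (BAT steps, distress, SPQ, FSQ). SCR peaks are less exposed. Someone who knows they have the active site may expect to improve, and someone who knows they have the control site may not. That gap would be read as a treatment effect. No purpose stated in the plan requires the reveal before the last Day 4 visit.

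**Working it through.** **1. Is anyone left to unblind at the first reveal?**
The visit windows (OVERVIEW) are 1 to 2 days, 1 to 2 days, and 5 to 7 days. Day 1 to Day 4 therefore takes 1 + 1 + 5 = 7 to 2 + 2 + 7 = 11 days. Unless all Day 4 visits fall together, some participants still have outcome visits ahead when the first is told. That new participants also start after this point is an inference, because no enrolment calendar is given. As an illustration, assume 1 to 2 starts per week:
- 1 per week, 7 days: first participant + 1 = 2 started, 40 − 2 = 38 not started.
- 2 per week, 11 days: first participant + 2 × 11/7 ≈ 3 gives 4 started, 40 − 4 = 36 not started.

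These are people who could be reached, not people who were told.

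**2. How much does the reported blinding check rule out?**
Assumptions: one active/control guess per participant, and a 1-df chi-square test of the number correct against 50/50, uncorrected, at 0.05. It rejects when (k − n/2)² / (n/4) > 3.84. If a share c of participants know their arm and the rest guess at 50%, then P(correct) = 0.5 + 0.5c. Power is the exact binomial probability of the rejection region.

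| Share knowing, c | P(correct) | Power, n = 20 (reject ≥15 or ≤5) | Power, n = 30 (≥21 or ≤9) | Power, n = 40 (≥27 or ≤13) |
|---|---|---|---|---|
| 10% | 0.55 | 6% | 7% | 8% |
| 20% | 0.60 | 13% | 18% | 21% |
| 30% | 0.65 | 25% | 36% | 44% |
| 40% | 0.70 | 42% | 59% | 70% |
| 50% | 0.75 | 62% | 80% | 90% |

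With 40 answers, 26 correct (65%) would still count as non-significant: (26 − 20)²/10 = 3.6. Under the model, 65% correct corresponds to c = 2 × 0.65 − 1 = 0.30. The planned n is 40. The note calls the sample small, so the number answering may be lower.

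**3. What could leakage do to a comparison? (illustration only)**
Let g be the between-arm expectancy gap, in SD, among those who know, with c equal in both arms. Bias = c × g. With 20 per arm, the SE of the difference is √(2/20) = 0.316 SD. The two-sided type I error is 1 − Φ(1.96 − bias/0.316) + Φ(−1.96 − bias/0.316).

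| c | g = 0.3: bias (type I) | g = 0.5 | g = 0.8 |
|---|---|---|---|
| 10% | 0.03 (0.051) | 0.05 (0.053) | 0.08 (0.057) |
| 20% | 0.06 (0.054) | 0.10 (0.062) | 0.16 (0.080) |
| 30% | 0.09 (0.059) | 0.15 (0.076) | 0.24 (0.118) |
| 50% | 0.15 (0.076) | 0.25 (0.124) | 0.40 (0.244) |

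Both c and g are assumptions. For scale, 20 per arm detects (1.96 + 0.84) × 0.316 ≈ 0.89 SD at 80% power (normal approximation). The plan gives no power calculation to compare with this.

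**The case against.** A reader might infer that the participant-driven primaries lost their blind, or that the collected results are tilted towards active iTBS. The documents do not support either. The only evidence they hold on the matter is the blinding check, which covered subjects and raters and found no significant departure from 50/50. If about 40 answered, that argues against half the sample knowing, so the bottom row of the last table is the least plausible.

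Other points also count against a strong claim:
- Disclosure follows the participant's own SPQ, FSQ and BAT, so it cannot affect their data. The earliest participants could not have been reached at all.
- Having a separate un-blinded team member do the debriefing suggests that blinded and unblinded roles were kept apart.
- A leak needs a debriefed student to meet someone still in the study, mention coil position, and be believed. The size of the pool and how well its members know each other are not given.
- The consent pages are not in the text reviewed and no debriefing script is reproduced, so a request for confidentiality may exist.
- This is a small pilot, and at 10% to 20% leakage the illustrative bias is small against a standard error of 0.316 SD.
- The 2/2/21 note describes analyses already done, so rewording Day 4 cannot protect those data.

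All of this stands. It limits the point to a risk of unknown size. It does not remove the point, because the route to unblinding follows from the plan as written, and a non-significant check without counts cannot exclude leakage to a fifth or a third of participants.

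**Conclusion.** The point holds as an avoidable design risk, not as a demonstrated loss of blinding. It rests on three things in the text: individual disclosure at Day 4 with no stated deferral, recruitment from a single pool, and arms that differ by a perceptible coil site. It bears on four of the five primary outcomes, and only through participants who had not completed Day 4.

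The reassurance available is limited. Under the stated model the blinding check has about 21% power at n = 40 if 20% know their arm (13% at n = 20), and about 90% if half know (62% at n = 20). It speaks against widespread unblinding if about 40 answered, but not against moderate leakage.

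No bias figure can be taken from the documents. Enrolment pace, the share told and the expectancy effect are all assumed here. The case for acting rests on how cheap the change is, not on the size of the effect.

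**What to change.** For any continuation or successor study, amend the DAY 4 text. Keep the debriefing and the opportunity for questions, but withhold the group until the last enrolled participant has completed the Day 4 questionnaires and BAT, then inform everyone. Ask participants at Day 4 not to discuss coil position with other students, if the consent form or debriefing script does not already do so. The cost is a short wording change, with matching consent text if the consent form promises the reveal at Day 4, and participants wait longer to learn their group.

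For the data already collected, report the number answering the blinding questionnaire and the guesses by arm and by enrolment order. The split by arm matters because, with equal arms, a shared tendency to guess active leaves the pooled rate at 50%. The split by order matters because leakage could only raise correct guesses among later participants, and pooling dilutes this. This needs only a tabulation of data already held.

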must be completed before moving on to the next step, and steps much be completed in sequential order. During each step, your heart rate and sweating will be recorded via the electrodes on your chest and finger. After the experimenter reads the instructions for the next step and prior to completing the step, you will also be asked to rate your confidence level to complete the step on a scale from 0 to 100 (0= no confidence, 25= mild confidence, 50= moderate confidence, 75= high confidence, 100 = complete confidence) and your anticipatory distress on a scale from 0 to 100 (0=no distress, 25=mild distress, 50=moderate distress, 75= high distress, 100= severe distress). After completion of each step, you will be asked to rate your maximum level of distress during the step on a scale from 0 to 100. You are entitled to withdraw at any step if you do not wish to continue. Do you have any questions before we begin? The first step of the experiment is to stand 5 feet away from the tarantula while it is in its closed container for 30 seconds. The final step of the experiment is to touch the back of the tarantula's leg with the tip of your index finger continuously for 30 seconds." Before beginning the BAT and after ensuring comprehension of the above instructions, the experimenter will ask the participant to rate his/her overall confidence and overall anticipatory distress with respect to his/her ability to complete all nine steps (see rating scales in above instructions). Before each subsequent step, the participant will be asked to rate his/her confidence and anticipatory distress regarding his/her ability to complete that particular step. During each step, the experimenter will record the spider's movement on a categorical scale (0 = no movement, 1 = a little movement, 2 = a lot of movement). After each step, the participant will be asked to rate his/her maximum level of distress while completing that particular step. Finally, the experimenter will record the number of steps willingly completed for a given participant.

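### The primary outcome for distress during the BAT is not tied to one rating or one test, so more than one result at p<0.05 could be claimed as that primary

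*Combined protocol and SAP*

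**What the plan says.** **DAY 4, dependent variables.** The list contains "self-reported distress, anticipatory distress, and maximum distress per BAT step". Read as a list, that is three distress variables.

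**DAY 4, primary outcomes.** "Primary outcomes examined will be number of steps completed during BAT, self-reported distress during BAT", followed by SCR peaks, SPQ and the fear-of-spiders score, which makes five primaries. Then: "All other variables examined will be secondary outcomes". For measures taken at each BAT step, "minima, maxima, and means will be compared between the two groups". A pre-comparison ANOVA is promised against multiplicity, without its factors, its outcomes or its decision rule.

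**DAY 1, BAT procedure.** Two distress ratings are taken per step, each on a 0 to 100 scale. One comes before: "Before each subsequent step, the participant will be asked to rate his/her confidence and anticipatory distress regarding his/her ability to complete that particular step". One comes after: "After each step, the participant will be asked to rate his/her maximum level of distress while completing that particular step". There is also a single overall anticipatory rating before the first step. No rating carries the plain name used for the primary.

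**Note of 2/2/21.** It replaces the t-test plan, says that the number of tests was kept down, and reports mixed models for "Behavioral measures acquired during the BATs (anticipatory distress, maximum distress, mean skin conductance at each step") as functions of step, group and timepoint. It applies p<0.05 to all testing and labels neither distress rating as primary.

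**The concern.** A primary outcome should lead to one number that decides it. Here the label does not lead to one rating. The variable list separates it from both ratings that are collected, and the rule on secondary outcomes would, taken at its word, put both of those ratings in the secondary tier. The note does not settle the matter: it analyses both ratings side by side and names no deciding term in either model.

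Timing makes this matter more. The note is written in the past tense and gives the observed data distributions as one reason for changing the analysis. Nothing written before that point fixes which distress result counts, so a favourable result on either rating could be presented as the primary. This is separate from having five primaries, because it adds chances within one of them.

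**Working it through.** **What the documents give.** No effect size, power or error rate is stated for the distress comparisons, so there is no figure of the plan's own to reproduce. The only stated level is 0.05 per test, in the note. The DAY 4 section gives 40 participants, 20 per group.

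**Counting the candidate tests.**

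| Reading | Count |
|---|---|
| Note: two ratings, one test per model | 2 |
| DAY 4 plan: 2 ratings × 3 summaries | 6 |
| DAY 4 plan, if only maximum distress is meant: 1 × 3 | 3 |

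The overall anticipatory rating would raise six to seven. Two and six belong to different versions of the analysis and must not be added. Two is also a minimum, since each model contains step, group and timepoint and more than one term could be read as the treatment effect.

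**Chance of at least one false positive, independent tests.** 1 − (1 − 0.05)^k.
- k = 2: 1 − 0.95² = 0.0975
- k = 3: 1 − 0.95³ = 0.143
- k = 6: 1 − 0.95⁶ = 0.265

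**Correlated tests.** Ratings from the same person at the same steps will correlate, so the independent figures are too high. The documents give no correlation; the range r = 0.5 to 0.9 is an assumption. For k two-sided z tests with common correlation r and c = 1.96:

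1 − ∫ φ(u) [Φ((c − √r·u)/√(1 − r)) − Φ((−c − √r·u)/√(1 − r))]^k du

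| k | r = 0.5 | r = 0.7 | r = 0.8 | r = 0.9 |
|---|---|---|---|---|
| 1 | 0.050 | 0.050 | 0.050 | 0.050 |
| 2 | 0.091 | 0.084 | 0.078 | 0.070 |
| 3 | 0.125 | 0.109 | 0.098 | 0.084 |
| 6 | 0.207 | 0.164 | 0.139 | 0.108 |

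**Check at the planned size.** A simulation of t-tests with 20 per group (20,000 runs) gave 0.093 (r = 0.5) to 0.068 (r = 0.9) for two tests, and 0.213 to 0.111 for six. The small sample does not change the picture.

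The six-test row gives every pair the same correlation and counts the minimum in full. The minimum will usually come from the first step, five feet from a closed terrarium, and probably adds little. Leaving it out (four tests) gives about 0.156 to 0.094. None of the DAY 4 figures allows for the pre-comparison ANOVA, whose effect cannot be calculated from what is written.

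**The case against.** The strongest reply is that the intended rating is plain enough. Maximum distress, rated after each step about the step just done, is a self-report of distress during the BAT. A reader might infer from the variable list that this primary has no data at all. The documents do not support that: a rating that fits the label is collected at each completed step, so the fault is an ambiguous label. What stands is that the list places maximum distress beside self-reported distress as a different item, and no later text equates them.

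A second reply is that the six-comparison plan was replaced. This is correct. A reader might take 21% as the error rate of the current plan, but the note reports mixed models over steps instead of t-tests on three summaries. The DAY 4 plan also included an ANOVA step meant to limit this error, and the 0.05 level is stated only in the note. The six-test figure therefore describes the superseded analysis, with its safeguard left out because it is unspecified.

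A third reply is that this is a small pilot meant to collect preliminary data. That limits how much rests on any single p-value. It does not remove the need to say which result answers a named primary.

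**Conclusion.** The concern holds as a defect of definition. The distress primary is linked to no single rating and no single test, and the note of 2/2/21 leaves both open. Under the note, the false-positive chance for this primary is about 9% to 7% instead of 5%, assuming a correlation of 0.5 to 0.9 between the ratings and one test per model. It would be higher if more than one term per model could be claimed. The DAY 4 comparisons of three summaries for both ratings would have given about 21% to 11%, before any effect of the ANOVA.

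These figures describe what the wording permits. The documents do not show that a rating was in fact picked by its result. Nor can new wording now restore prespecification, because the analysis was revised after the data were seen.

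**What to change.** - In the DAY 4 section, define this primary as maximum distress rated after each BAT step, which is the rating that refers to the step itself.
- Name one deciding term in the mixed model: group by timepoint. This matches the Project Summary, which compares pre-to-post change between groups. The note names no term at present.
- Label anticipatory distress, and the comparisons of minima, maxima and means, as secondary.
- State how steps not completed enter the model. Maximum distress is rated only after a completed step, participants may withdraw at any step, and the number of steps completed is itself a primary. The missing ratings are therefore unlikely to be unrelated to fear.
- Report both ratings in full, claim the primary only on the named one, and disclose that the choice was made after the data were seen and is not prespecified.

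The naming and labelling need only new wording, with no new data. Two costs follow: one fewer result can be called primary, and the chosen rating is missing for refused steps, whereas the anticipatory rating is asked before the step is attempted.
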